What are the specific scientific objectives of the research?

This study aims to evaluate the feasibility and compare the preliminary effect of vaping

cessation program consisting of media literacy education and real-time text messaging support and leverage insights from behavioral economics to enhance financial incentives to improve program engagement, and eventually abstinence. Our hypotheses are that 1) the *Combined* arm is associated with improved vaping abstinence to the *Media literacy and Financial incentive* arms; and 2) the financial incentive-related arms (either *Combined* or *Financial incentive*) enhance engagement compared to the non-incentive related arms.

3. Background and Rationale

Describe the background of the study. Include a critical evaluation of existing knowledge, and specifically identify the information gaps that the project is intended to fill.

Vaping has become a public health crisis among youth/young adults.¹ In 2020, an estimated 19.2% of U.S. high school students and 9.4% of young adults aged 18-24 years old reported current use of e-cigarettes.^{2,3} For these emerging vaping products with varying devices and nicotine formulations, the health effects of vaping and vaping cessation remains largely unknown.⁴ E-cigarette use among young people may also increase the risk of nicotine addiction and transition to cigarette smoking, marijuana, and other substance use.^{5,6} In 2020, 53.4% of current young e-cigarette users reported intention to quit vaping, and 67.4% reported having tried to quit vaping,⁷ but failed attempts to quit vaping remained high.⁸ Very limited evidence-based vaping programs have been developed,⁹ and the program reach continues to be an implementation issue for evidence-based programs (EBPs), especially among youth/young adult populations.¹⁰

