A. Will adults be enrolled ?

Yes

1. What is the age range of the adult subjects?

Young adults aged 19-29

2. What is the rationale for selecting this age range?

As vaping is prevalent in youth and young adult population, the objective of this study is to test the application of financial and social support to improve the reach, engagement and retention of the vaping cessation program consisting of education lessons and text-messaging support program, which are developed and tested specially among youth and young adult populations.

In general, young adults are referred to adults aged between 18-20 years-old. In Nebraska, an individual is considered an adult when he/she reaches the age of 19.

B. Will children (18 years of age or younger) be included in this research?

No

1. What is the justification for excluding children from participating in this research?

Research is irrelevant to children (e.g. disease or condition rarely encountered in children). Knowledge being sought in the research is already available for children or will be obtained from another ongoing study.

♦ A separate study in children is warranted and preferable.

Insufficient data are available in adults to judge the potential risk in children.

Other. Explain.

7. Race and Ethnicity

Are there any subject enrollment restrictions based upon race or ethnic origin?

No

8. Vulnerable Subjects

A. Will prisoners be included in the research?

No

B. Select from the list all of the vulnerable populations that will specifically be recruited to participate in this research.

Decisionally-impaired persons

Critically ill patients

Students of the investigator

Employees of the investigator

Educationally disadvantaged individuals

Socially or economically disadvantaged individuals

Individuals with a stigmatizing illness or condition

Individuals from a marginalized social or ethnic group

Other.

♦ No vulnerable subjects will be specifically recruited

9. Inclusion Criteria

What are the specific inclusion criteria?

- Aged 19-29
- Self-report current e-cigarette users (in the past 30 days)
- Have access to internet/video chat/SMS text message
- Are interested in quitting vaping in the next 30 days

10. Exclusion Criteria

What are the specific exclusion criteria?

- Must meet all the inclusion criteria
- Self-report as currently pregnant or planning to become pregnant in the next 3 months
- Already involved in vaping cessation programs (either behavioral or medical intervention)

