2. Baseline and end-of-study survey, including demographic, vaping history, vaping experience/behavior, attempt to quit, Penn State Nicotine Dependence Index, exposure to Tobacco Marketing and Marketing Influences, UPPS impulsive behavior scale, money choice question, and self-efficacy about not to vape, and wheezing and related respiratory symptoms

Primary outcome

- **biochemically verified vaping abstinence** (negative results- will be cut-off < 30 ng/mL⁷¹), measured by saliva cotinine samples at the Week 12 visit.

Secondary outcome

1. Nicotine abstinence: bi-weekly/monthly saliva nicotine abstinence results (positive vs. negative) will be obtained using the iScreen test kit ([https://stat-technologies.com/product/alere-iscreen-for-cotinine/#:~:text=The%20Alere%20iScreen%C2%AE%20OFD,nicotine\)%20in%20human%20oral%20fluid.](https://stat-technologies.com/product/alere-iscreen-for-cotinine/#:~:text=The%20Alere%20iScreen%C2%AE%20OFD,nicotine)%20in%20human%20oral%20fluid.)) after the target quit date for 2 month in addition to baseline and Week 12 saliva cotinine samples. Saliva sample/results will be collect in person at baseline and Week 12 visits and remotely via live video calls during the abstinence phase. The remote saliva sample collection will follow the instruction below:

- Participants will open the new, labeled packaging for each testing kit while on the video call to ensure they are using a new test each time
- Participants will be asked to write down the participants id, test number, date, and time on the test kit
- Participants will take a picture, including participant id, test number, date, and time for verifying the final results and provide the final results and picture to the research

staff before ending the call (approximately 10-minute processing time) All participant will need to provide a saliva sample at the in-person baseline and the Week 12 visits and at remote video calls (Week 6, Week 8, and Week 10).

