2. Biomarkers of toxic exposures: Twenty participants who are assigned the biomarker measurement group will need to provide the urine sample at the in-person baseline (Week 0) and Week 12) visits at the UNMC clinical research center (CRC). The nurse research coordinator at CRC would assist with the urine sample collection. The biomarker classes may include: 1) cotinine and hydroxycotinine, and 2) creatinine. The biomarker testing of toxic exposure is solely for research purpose and thus the results will not be share with the participants.

3. Engagement, assessed by: a) proportions of media literacy e-learning lessons completed at the end of the quitting preparation phase (Week 4), and b) proportions of participants who submitted the remote saliva cotinine sample at each scheduled time-point at Week 12;

4. Nicotine dependence index, measured by the Penn State E-cigarette Dependence (PSECD) index at baseline and Week 12;

5. Media literacy, measured by the vaping media literary scale at baseline and Week 12.

4) Self-reported vaping abstinence, assessed by the question In the past 30 days, did you vape at all, even a puff of someone else? at Week 12.

Exploratory outcomes

We will collect intervention cost data using all program invoices related to program implementation and survey questionnaire to estimate the cost-effectiveness of the program. For example, we will calculate the incremental cost per additional completing the vaping cessation program, the incremental cost per additional abstinence case across study arms.

C. Select any of the following that apply to the research:

Phase I study

♦ Randomization

Placebo (or non-treatment arm)

Washout

Sensitive surveys or questionnaires

None of the above

Option chosen: Randomization

Describe randomization process and schedule

Participants will be assigned following a randomization table created by the study statistician after completing the consent process and baseline survey on the REDCap platform. To

ensure an even distribution of participants between the four intervention groups, eligible subjects will be randomly assigned to one of four intervention groups using a computer generated randomization table created by the study statistician. We will recruit 5 participants from each intervention group (until fulfilled) for the biomarker measurement group.

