Upon randomization, research staff will review the intervention component based on the intervention group that they are assigned to with the participants and provide instruction and materials for the followup sessions.

D. Identify:

1. All procedures, interventions, evaluations and tests performed solely for research purposes (eg, administration of an investigational drug or a new psychological assessment instrument; randomization)

- We will administer a set of educational lessons about vaping cessation that discuss what e-cigarettes are and how they work, how nicotine and nicotine addiction affects the brain and behavior, how to prepare to quit vaping, developing a quit plan and how to deal with cravings and relapse.
- We will facilitate participants to download and enroll in the evidence-based vaping cessation support text-messaging program (This is quitting, <https://truthinitiative.org/thisisquitting>)
- We will administer monetary incentives based on engagement (submitting saliva samples at Week 6, Week 8, and Week 10), and the efforts with vaping cessation (abstinence results).
- We will evaluate nicotine levels in the body for program efficacy via 5 saliva sample (2 at in-person baseline and Week 12 visits and 3 at check-in video calls at Week 6, Week 8, and Week 10); and two urine cotinine tests for biomarker of toxic exposure (only for 20 participants in the biomarker measurement group) at in-person baseline and Week 12 visits)
- We will administer a set of screening questions, baseline/end-study surveys, and vaping-related symptom questionnaires (e.g., wheezing and related respiratory symptoms)-only for 20 participants assigned to the biomarker measurement group).
- For quality improvement and future modification and adoption of vaping cessation programs, we will conduct an exit interview with participants (n=8-12; n=2-3 from each arm based on first available participants) who have completed the final study visit through a video call. We will assess the feasibility, facilitators, and barriers to participation and engagement in the study's vaping cessation interventions.

2. All procedures, interventions, evaluations and tests performed for clinical indication but more frequently than they would be if the subject was not participating in the research (eg, extra blood tests; additional radiology exams)

None.

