UNMC offers a nicotine dependence clinic (cigarettes, dip, other forms of nicotine products) that has dependence counseling services with a qualified professional. Clinicians at this clinic offer counseling, pharmacotherapy (nicotine replacement therapy), and lung screening for high-risk patients. Services are offered at a cost.

2. Is the potential benefit of the research at least as good as the potential benefits of the alternatives described above?

Yes

3. Are there any reasonably available alternatives outside this institution which would have the potential for providing benefit to the subjects outside the research context?

Yes

a. What are the reasonably available alternatives?

Other institutions have similar nicotine dependence clinics similar to the clinic described above.

4. Would any of the study procedures or courses of treatment in the protocol be available to the subject if they elected not to participate?

Yes

a. Explain.

Participants who choose not to participate or withdraw from the study, will still have access to the SMS text-based quitting support program (This is Quitting), and cotinine testing (saliva samples).

5. Would the research intervention be available outside the context of research?

Yes

6. Are there any treatments that the subject would be denied as a consequence of participating in research that he/she would have received had he/she not participated?

No

7. How do the risks of the research compare with the risks of alternative procedures or courses of treatment described above?

There are some risks associated with pharmacotherapy (nicotine replacement) treatment that may be applicable to the treatment options mentioned above. Given that this study simply includes ono-invasive interventions- media literacy e-learning lessons, text-messaging support programs, and financial incentives, the risk of research is minimal or

comparable to the risk of alternate procedures.

FINANCIAL OBLIGATIONS AND COMPENSATION

22. Financial Obligations of the Subject

A. Who will pay for research procedures, interventions, evaluations and tests? Check all that apply.

Sponsor

◆ Grant

CRC, CCTR

Costs or fees waived by Nebraska Medicine, UNMC- P, CHMC or CSP

Department/Section funds

◆ Other. Explain faculty fund

B. Will any of the research procedures, interventions, evaluations and tests described above be charged to the Subject, the Subject's health insurance, or Medicare/Medicaid?

No

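### The primary outcome is called vaping abstinence but is only a Week 12 cotinine below 30 ng/mL, so a participant who reports vaping can count as a success

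*Combined protocol and SAP*

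**What the plan says.** Section 12.B (Primary outcome) defines success as a negative cotinine, with a cut-off of 30 ng/mL, "measured by saliva cotinine samples at the Week 12 visit". It sets no self-report condition.

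Self-reported vaping is a separate secondary outcome at Week 12, based on the question "In the past 30 days, did you vape at all, even a puff of someone else"?

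The name of the target varies. In Section 2 the hypothesis is that the Combined "arm is associated with improved vaping abstinence to the" two single-component arms. Secondary outcome 1 uses the same kind of test under another name: "Nicotine abstinence: bi-weekly/monthly saliva nicotine abstinence results (positive vs. negative) will be obtained using the iScreen test kit". Section 12.D.1 says "We will evaluate nicotine levels in the body for program efficacy via 5 saliva sample".

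Section 9 admits people who report e-cigarette use in the past 30 days and who "Are interested in quitting vaping in the next 30 days". It sets no minimum frequency, nicotine content or cotinine level. Section 10 excludes people already in a vaping cessation programme, but not users of other tobacco. A saliva sample is taken at baseline. Section 12.E adjusts for age, gender and race/ethnicity only, and gives no rule that links self-report to cotinine.

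**The concern.** The label and the measure describe different things. A cotinine result shows recent nicotine exposure relative to a cut-off, whereas the hypothesis is about vaping. Because entry is open to infrequent vapers and to people who vape without nicotine, some participants may be below 30 ng/mL before they change anything. Such a person could keep vaping, say so at Week 12, and still be a primary success.

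The gap also runs the other way. Cotinine reflects nicotine from any source, so a participant who stops vaping but uses another nicotine product counts as a failure.

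What is at stake is mainly the abstinence rate in each arm. Section 4.A.2 says the pilot is to inform scaling to a larger group, and the exploratory outcomes include a cost per additional abstinence case. A rate that mixes stopping vaping with nicotine status is a weak basis for either.

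**Working it through.** **Plan's own figure.** 4 arms × 20 = 80, as stated in Section 4. The plan gives no abstinence rate, effect size or power, so there is nothing further to reproduce.

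**Reading the rule.** Applying the definitions in Section 12.B at Week 12:

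| 30-day question | Cotinine | Primary outcome | Self-report outcome |
|---|---|---|---|
| no vaping | below 30 | success | success |
| vaping | below 30 | success | failure |
| no vaping | 30 or more | failure | success |
| vaping | 30 or more | failure | failure |

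The second row is the concern. The third row includes quitters who use another nicotine source. No section says how either discordant row should be read.

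**Size: inputs.** All are assumptions.
- p: true vaping abstinence, taken as 20% v 40%.
- f: share who test below 30 at Week 12 whether or not they vape.
- p is taken to be the same in low-exposure and other vapers.
- Other nicotine use is set to zero.

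**Formula.** Cotinine-only rate = f + (1 − f)p = p + f(1 − p). The excess is f(1 − p).

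**Equal f in both arms.**
- f = 5%: 0.05 + 0.95 × 0.20 = 24%, and 0.05 + 0.95 × 0.40 = 43%. The difference is 19 points.
- f = 10%: 0.10 + 0.90 × 0.20 = 28%, and 0.10 + 0.90 × 0.40 = 46%. The excess is 8 and 6 points, and the difference is 18 points. In an arm of 20 this is 1.6 and 1.2 false successes.

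At the same incremental cost, cost per additional abstinence case is multiplied by 1/(1 − f): 1.05 at f = 5% and 1.11 at f = 10%.

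**Unequal f.** Only the two incentive arms are paid for negative samples (Section 12.B, Financial incentive), so f could differ by arm. Keep f = 10% in the unpaid arm.
- Paid f = 15%, true 20% v 20%: 28% v 0.15 + 0.85 × 0.20 = 32%, a spurious 4 points.
- Paid f = 15%, true 20% v 40%: 28% v 0.15 + 0.85 × 0.40 = 49%. The difference is 21 points, and the cost multiplier is 20/21 = 0.95.
- Paid f = 5%, true 20% v 40%: 28% v 43%. The difference is 15 points, and the cost multiplier is 20/15 = 1.33.

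Once errors differ by arm, neither direction is fixed.

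**If low-exposure vapers quit at their own rate q.** The excess is f(1 − q). At f = 10% it is 8, 6 or 4 points for q = 20%, 40% or 60%.

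**Random error for scale.** The 95% half-width for 20% v 40% at 20 per arm is 1.96 × √(0.2 × 0.8/20 + 0.4 × 0.6/20) = 0.277, about ±28 points.

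**What a two-part outcome would read.** Let u be the share of low-cotinine vapers who deny vaping. The rate is p + f(1 − p)u. At f = 10% and p = 20% it is 20% if u = 0, 22% if u = 25% and 24% if u = 50%, against 28% for cotinine alone.

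**Window.** Week 12 is day 84, and 84 − 30 = day 54. The latest permitted quit date is about day 30 or 31 (Section 12.B, Goal setting and Measurement), so the 30-day question covers only time after it.

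**The case against.** The strongest reply is that biochemically verified already implies a self-report that cotinine then confirms. The text does not say so, and it lists self-report as its own outcome. If that was the intent, a sentence is still needed, because two analysts could code the outcome differently.

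A second reply is that an objective, test-based endpoint suits an intervention that pays for negative tests, and that self-report from unmasked participants (Section 18.B) brings its own error. This stands as an argument for keeping cotinine alone, but then the outcome should be named for what it measures.

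A third is that the pieces are already planned: self-reported abstinence at Week 12, repeated cotinine, vaping frequency at screening and vaping behaviour in the surveys. This also stands. What is missing is the link between them.

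Three stronger readings are tempting but not supported:
- A reader might infer that the error overstates cost per case, or that it favours the paid arms. The first needs equal errors across arms. The second needs payment to change the errors in one direction. The documents establish neither.
- A reader might infer that nicotine replacement is expected during the trial. Section 21 item 1 describes it as care a person might receive outside the study. Item 6 says only that participants are denied no treatment, and Section 10 excludes people already in a cessation programme at entry. Other tobacco use and later nicotine use remain possible, but nothing indicates how common they are.
- A reader might infer that the arm comparison is seriously distorted. At f of 5% to 10%, equal in both arms, it moves by 1 to 2 points against ±28.

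**Conclusion.** The point holds as a mismatch between label and measure. Under the written rule, a participant who reports vaping and tests below 30 ng/mL is a primary success, and no other section repairs this. That conclusion rests on the text alone.

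Its size rests on assumption, because the documents give neither f nor any abstinence rate. At f = 10% each arm's rate is 6 to 8 points too high for true rates of 40% and 20%. With equal errors, the difference falls from 20 to 18 points and cost per additional case is multiplied by about 1.11. With unequal errors, the direction of both biases is unknown. The shift in the arm difference is small beside the sampling error of this pilot, so the main consequence is for the level of the abstinence rate and what it means. Misclassification of quitters who use other nicotine is a further, unquantified limit.

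**What to change.** Choose one target and state it in Section 12.B.

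- **If vaping is the target:** define primary success as a negative answer to the existing 30-day vaping question and cotinine below 30 ng/mL, both at Week 12. Keep cotinine alone as the nicotine-abstinence secondary outcome. Treat a participant missing either component by the same rule as a missing sample. Section 12.E states no such rule, so it has to be written.
- **If nicotine status is the target:** relabel the primary outcome as nicotine abstinence and align the hypothesis in Section 2.

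In either case add two items:
- A table of self-report by cotinine at Week 12, by arm.
- A sensitivity analysis limited to participants who were cotinine-positive at baseline. At an assumed baseline-negative share of 5% to 10%, only 20 × 0.05 = 1 to 20 × 0.10 = 2 people per arm would be left out, so it is descriptive.

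The cost is outcome wording, a missing-data sentence, one table and one extra analysis. No visit, sample or question is added, and the payment rule is untouched.

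The two-part definition has downsides: a lower abstinence rate, a stricter criterion under which a single puff in 30 days is a failure, and partial reliance on unmasked self-report. It removes false successes only as far as answers are truthful, and it does not correct for quitters who take nicotine from another source. Relabelling avoids these downsides but changes what the trial claims to measure.

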The objective of this pilot study is to evaluate the feasibility and compare the potential effect of different vaping cessation intervention components in addition to evidence-based text-messaging support, including 1) media literacy interactive e-learning lessons, 2) financial incentives, and 3) combined (media literacy + financial incentive) on vaping abstinence among current young adult vapers over a three-month timeframe with the following three specific aims: Aim 1. To assess the feasibility of a multi-component vaping cessation program; Aim 2 To evaluate the preliminary effect of a multicomponent vaping cessation program; and exploratory Aim 3. To Examine the cost-consequence of a multicomponent vaping cessation program. Eligible participants are young adults aged 19-29 and are current vapers (i.e., using e-cigarettes in the past 30 days). We will employ a 4-arm, feasibility randomized trial design to determine the preliminary effect of different vaping intervention components on vaping abstinence over a 3-month timeframe, consisting of a 1-month quitting preparation phase and 2-month abstinence phase. Eligible participants (n=80) will be randomized (in a 1:1:1:1 ratio), using a computer-generated algorithm, to one of four vaping cessation interventions: 1) Active control: text-messaging support, 2) Media literacy: media literacy + text-messaging support, 3) Financial incentive: financial incentive + text-messaging support, and 4) Combined: media literacy e-learning lessons + financial incentive + text-messaging support, at the baseline visit. Regardless of intervention arms, all enrolled participants will receive an evidence-base text-messaging support program for quitting vaping (This is Quitting). Participants will be followed through a 3-month study period including a 1-month quitting preparation phase and a 2-month abstinence phase. All participants will be asked to provide 5 saliva cotinine samples- at baseline and end-of-study visits and 3 at video calls (remote submissions). Participants who assigned to the financial incentive Combined groups will be provided monetary rewards for submitting saliva cotinine samples during the abstinence period. To examine the feasibility of biomarker testing for toxic exposures, for a subsample of 20 participants, a panel of biomarkers of toxic exposures will be measured at baseline and at the end of study.

PURPOSE OF THE STUDY AND BACKGROUND

2. Purpose of the Study

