Contingency management is an established behavioral intervention in which individuals receive reinforcement (e.g., financial incentives) contingent upon biochemically verified abstinence.¹¹ Incentives have been used to encourage healthy behaviors,¹² and as an implementation strategy to improve EBP reach and engagement.¹³ Moreover, social support has been integrated into smoking interventions to promote cessation.¹⁴ Notably, family and friend use is one of the top reasons for youth to use e-cigarettes¹⁵, and vaping for entertainment is common among young vapers.¹⁶ Studies have shown that peer support can be an effective strategy in increasing social support and promoting abstinence in smoking cessation, especially among young people.^{17,18} Although there is clear evidence that social support and financial incentives individually improve smoking cessation rates in mixed population,¹⁹ little is known regarding their individual and collective effect on vaping cessation program reach and effectiveness, especially targeting the young adult population.^{10,20}

CHARACTERISTICS OF THE SUBJECT POPULATION

4. Accrual

A. Is this study conducted solely at sites under the oversight of the UNMC IRB (e.g.

UNMC, Nebraska Medicine, CHMC, UNO)?

Yes

1. How many subjects will need to be consented (per group, as applicable) in order to achieve the scientific objectives of the research?

We will recruit 80 young adult current vapers aged 19-29 to test a four-arm pilot trial (*Active control, Media literacy, Financial incentive, and Combined*) with n=20 for each arm.

2. What is the statistical or other justification for the total number of subjects described above?

As this is a pilot feasibility study, and as the rule of thumb, it was suggested that a minimum sample size of 12 subjects per treatment arm or a total sample size of 70 in order to reduce the imprecision around the estimate of the standard deviation for a pilot trial. Accordingly, the sample size of 80 for this study would be sufficient to assess the preliminary effectiveness of financial and social incentives as well as determine the feasibility and ability to scale interventions to a larger group.

3. How long do you estimate it will take to accrue the required number of subjects?

We estimate that it will take about 3-4 months to accrue the required number of subjects.

5. Gender of the Subjects

A. Are there any enrollment restrictions based on gender?

No

6. Age Range of Subjects

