Interested individuals will complete an online screening through RedCap to determine their eligibility prior to informed consent. Screening questions includes current age, frequency of vaping, access to internet/video chat/SMS text message or not, and intention/desire to quit.

B. Will the investigator make the initial contact with the potential subject to tell him/her about the research (for example, by contacting existing or past previous patients or research participants; or by contacting prospective subjects thru school records, or thru support groups or other Interest Groups; or thru use of the Hospital Opt-In Database)?

Yes

1. How will prospective subjects be identified?

We will work with UNMC EHR data access core to identify a potential participant pool. A recruitment/screening email will be sent to patients aged 19-29 with an opt-in for research indication through the Epic patient portal.

2. Will potential subjects be screened for eligibility prior to informed consent?

Yes

a. What information will be collected prior to informed consent?

Interested individuals will complete an online screening through RedCap to determine their eligibility prior to informed consent. Screening questions includes current age, frequency of vaping, access to internet/video chat/SMS text message or not, and intention/desire to quit.

b. By whom?

Interested individuals will complete an online screening through RedCap by themselves to determine their eligibility prior to informed consent. If an interested individuals contacts the research team because of the recruitment flyer or other mode (e.g., social media) outside of the recruitment email (e.g., see the flyer in the community), the research staff, listed on the IRB protocol will conduct the phone screening using the RedCap to determine his/her eligibility. If the individual is eligible, the research staff will obtain a verbal consent from the individual and enroll him/she in the study and email him/her a copy of informed consent.

c. Does that person have ethical access to information about potential subjects?

Yes

i. Describe

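### Neither the randomisation nor the planned regression uses vaping frequency, although it is known before allocation and is plausibly strongly prognostic for Week 12 cotinine

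*Combined protocol and SAP*

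**What the plan says.** **Allocation.** The study summary says participants "will be randomized (in a 1:1:1:1 ratio), using a computer-generated algorithm". Section 12.C adds: "Participants will be assigned following a randomization table created by the study statistician after completing the consent process and baseline survey". The stated aim is to "ensure an even distribution of participants between the four intervention groups, eligible subjects will be randomly assigned to one of four intervention groups". No stratum, block or minimisation factor is named in either place or in the enrolment description in section 12.B.

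**Size.** Section 4 says: "We will recruit 80 young adult current vapers aged 19-29 to test a four-arm pilot trial", "with n=20 for each arm". The justification is a pilot rule of thumb, "a minimum sample size of 12 subjects per treatment arm or a total sample size of 70". No abstinence rate, target effect or power is given.

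**Who enters.** The criterion on use in section 9 is "Self-report current e-cigarette users (in the past 30 days"). There is no minimum frequency and no baseline cotinine level. A separate criterion requires interest in quitting within 30 days.

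**What is known before allocation.** Section 25 lists: "Screening questions includes current age, frequency of vaping, access to internet/video chat/SMS text message or not, and intention/desire to quit". The baseline survey, also completed before allocation, covers vaping history and behaviour.

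**Endpoint and analysis.** The primary outcome (section 12.B) is binary: saliva cotinine below 30 ng/mL at Week 12. Section 12.E plans chi-square and ANOVA comparisons and a multivariable regression adjusted for age, gender and race/ethnicity, with significance at p < 0.05.

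**The concern.** Daily and occasional users can both enter, and a negative cotinine test at Week 12 is plausibly a much harder target for a daily user. Baseline frequency is therefore an obvious candidate predictor of the primary outcome. It is in hand before allocation, yet neither the design nor the analysis uses it.

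With 20 per arm, one arm can by chance receive noticeably more occasional users than another, and nothing in the planned model would account for it. Aim 2, the first hypothesis (Combined against each single-component arm) and the exploratory cost per additional abstinence case all rest on between-arm differences in abstinence. A visible imbalance in this factor would make those estimates harder to interpret and harder to carry into a larger trial.

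**Working it through.** **1. The plan's own figure.** 4 arms × 20 = 80, which reproduces the stated total. It exceeds both rule-of-thumb minima (4 × 12 = 48, and 70 in total). The documents give no figure for imbalance, so the rest needs assumptions.

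**2. Inputs.**
- From the documents: 80 participants, arms of 20, binary endpoint.
- Assumed: share of daily vapers p = 50% (range 30-80%).
- Assumed: abstinence gap g, non-daily minus daily, of 20-30 points (range 10-40).
- Assumed for step 6: overall abstinence 25%.

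**3. Imbalance between two given arms.** With 80 people split into fixed arms of 20, the SD of the difference in daily share is

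SD = √[2p(1−p)/20 × 80/79].

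At p = 0.5: √(0.025 × 1.0127) = 0.159, or 15.9 points. The 95% limit is 1.96 × 15.9 = 31 points. Simulation with 200,000 draws agrees. For one given pair, the imbalance is at least 20 points in 27% of trials and at least 30 points in 8%.

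**4. Shift in the abstinence contrast** = imbalance × g.

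| p | g (points) | 1 SD (points) | 1.96 SD (points) |
|---|---|---|---|
| 50% | 20 | 3.2 | 6.2 |
| 50% | 30 | 4.8 | 9.4 |
| 80% | 10 | 1.3 | 2.5 |
| 50% | 40 | 6.4 | 12.5 |

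The last two rows are the extremes over the assumed ranges.

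**5. Effect of stratifying on imbalance** (simulated, p = 50%). Separate lists for daily and non-daily vapers in permuted blocks of 4 cut the SD of the pairwise imbalance from 15.9 to 2.3 points, with a maximum of 5. Randomly mixed blocks of 4 and 8 give just under 3 points, with a maximum of about 11.

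**6. Effect on precision.** At 25% abstinence the unstratified standard error of a 20 v 20 risk difference is √(2 × 0.25 × 0.75/20) = 13.7 points, a 95% half-width of about 27. With strata balanced and in the model, only within-stratum variance remains:
- g = 20 (15% v 35%): mean variance (0.1275 + 0.2275)/2 = 0.1775. SE = √(2 × 0.1775/20) = 13.3 points, half-width about 26.
- g = 30 (10% v 40%): mean variance (0.09 + 0.24)/2 = 0.165. SE = 12.8 points, half-width about 25.

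**The case against.** The strongest reply is that chance imbalance is part of what the standard error measures. Randomisation has expectation zero for it, the gain from stratifying is about half a point to one point of standard error, and contrasts of 20 v 20 stay very imprecise either way. The trial is a feasibility pilot seeking preliminary effects. All of this stands, and it limits the weight of the point. It does not remove the case for a change that costs almost nothing.

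A reader might infer more than the documents support:

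- **That contrasts are biased by 6-9 points.** The shift is random, not systematic. The figure is a 95% limit under two assumptions the documents do not supply.
- **That imbalances of 20 points or more are the norm.** At a 50% daily share, the gap between the most and least daily-heavy of the four arms is at least 20 points in about 69% of trials and at least 30 in about 31%. That describes the worst of six pairs, picked afterwards. The figures for one given pair are 27% and 8%.
- **That the list is unblocked and arm sizes will drift.** The documents never say so. A table with 20 entries per arm would satisfy the stated ratio, arm size and aim. What is missing is a statement of the method.
- **That the shift rivals the treatment effect.** No target effect is stated, so there is nothing to compare it with.

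The quit-interest criterion may narrow the mix of users, but it does not exclude occasional vapers. Adjusting for frequency without stratifying is a legitimate alternative that leaves allocation untouched. It handles a realised imbalance but does not prevent one.

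**Conclusion.** The point holds as a moderate weakness that should be corrected. A plausibly strong predictor of the primary outcome is known before allocation and is absent from both the randomisation and the adjustment set.

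Its size depends on two assumed quantities. At a 50% daily share and a 20-30 point gap, a given pairwise contrast typically moves by 3-5 points, with a 95% limit of 6-9. The wider ranges allow anything from a minor nuisance (1.3 points at 1 SD) to a material shift (12.5 points at the 95% limit). That frequency is prognostic is itself a judgement from the eligibility rule and the endpoint, since the documents give no abstinence rates by frequency. The finding concerns precision and interpretability. It does not make the planned comparisons invalid.

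**What to change.** In section 12.C, state that the statistician's table is stratified by daily v non-daily vaping, taken from the screening survey, and uses permuted blocks of randomly varied size (for example 4 and 8). Allocation after consent and the baseline survey is already specified and needs no change.

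In section 12.E, add the stratum as a covariate in the abstinence model. The precision gain needs both parts, because an analysis that ignores the stratum would not show it in the standard error.

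If stratification is declined, state the balancing method and pre-specify vaping frequency as a covariate.

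Cost: two lists instead of one, and arm totals that may differ by a few participants where blocks are left incomplete. Fixed blocks of 4 balance slightly better than mixed 4 and 8, but are easier to predict in an unmasked trial. The model gains one parameter, to be weighed against few events (25% of 80 = 20 at the assumed rate). No extra participants or data collection are needed.
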